10.4.3 Analysis of the secondary efficacy endpoints

A 6-participant phase I lead in cohort in advanced (castration resistant prostate cancer) participants will be conducted to determine safety. Once all 6 participants have completed a 6-week toxicity assessment period the toxicity data will be shared with IRB. If the IRB approves accrual to evaluate PSA response, then the trial will move forward with the planned study in biochemical recurrence. The participants in the safety cohort will only be analyzed for safety and toxicity, and not PSA changes.

Safety of the combination regimen will be assessed by reporting the grade of adverse events noted in each participant, and reporting the fraction with grade 3 and grade 4 adverse events.

To test for changes in PSA kinetics after treatment with the combination immunotherapy relative to baseline PSA kinetics, the changes in PSA over defined intervals (e.g., 1 to 3 months or similar) after administering the vaccines as well as after administering the checkpoint inhibitor will be determined by calculating the slope of the PSA change over time. Then, the slopes obtained after administering the vaccines alone or in combination with the checkpoint inhibitor will be tested vs. the slopes obtained prior to administering the vaccines using a two-tailed 0.05 significance level paired t-test or Wilcoxon signed rank test (if the paired differences are not normally distributed).

In addition, because a trial of participants with similar eligibility (16-C-0035) may result in approximately 36 participants who are undergoing surveillance for 6 months, this other trial may serve as a control for a secondary evaluation. The changes in PSA on this trial during the initial 6 months can be compared to the changes in PSA during the initial 6 months on the surveillance arm of the control trial as a secondary evaluation. The fractions of participants who experience a 30% PSA maximum change on the present study as well as the approximately 36 participants on 16-C-0035 who underwent surveillance will be compared using a one-sided significance level Fisher's exact test.

Please note: As of December 21, 2018, the 6 participants in the lead in cohort have completed the 6-week toxicity assessment period and no SAEs were seen. Per the protocol design participants will now be enrolled to the BCR cohort. The toxicity assessment of participants in the lead-in cohort is described in section **1.2.13.**

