10.2 SAMPLE SIZE DETERMINATION

The trial will begin with a 6-participant safety lead-in. Following determination of safety, the primary objective of this study is to determine if the use of two vaccines combined with an immune checkpoint inhibitor can be associated with a modestly high fraction of participants who can experience at least a 30% decline from their maximum PSA anytime during treatment to the minimum value during treatment.

Safety data for the 6-participant lead-in will be shared with IRB before accrual commences in the biochemical recurrence cohort. Beyond safety, this cohort will just be evaluated in a descriptive manner.

Because participants may be receiving the proposed treatment and be followed for PSA changes over an extended period, and the evaluation of the endpoint may take place at any point during this potentially long period, the trial will use a single stage design for evaluating efficacy. With 25 evaluable participants who do not receive M7824, there would be 82% power to rule out 15% and be consistent with 35% who may be able to experience a 30% decline in PSA, using an exact binomial test with a 0.10 one-sided significance level. As an illustration, if 25 evaluable participants are enrolled, 7 of 25 (28.0%) who experience at least a 30% PSA change from the maximum level would have an associated one-sided lower 90% confidence interval bound of 16.3%, and simultaneously an associated one-sided upper 90% confidence interval bound of 42.6%. These demonstrate that 7/25 would be a desirable result based on the parameters selected.

With the amendment v7/29/2021, the initial 6 participants who received M7824 will be evaluated separately in exploratory fashion and will not be included among the 25 main participants.

In addition, because a trial of participants with similar eligibility (16-C-0035) may result in approximately 36 participants who are undergoing surveillance for 6 months, this other trial may serve as a control for a secondary evaluation. The changes in PSA on this trial during the initial 6 months can be compared to the changes in PSA during the initial 6 months on the surveillance arm of the control trial as a secondary evaluation. With 25 evaluable participants on this trial and 36 evaluable participants on the other trial, there would be 81% power to identify a difference between 35% of participants on this trial with a 30% PSA maximum change and 10% of participants on the

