control trial with a 30% PSA maximum change with a 0.10 one-sided significance level Fisher's exact test.

It is anticipated that 1-2 participants per month can be enrolled onto this trial; thus, it is expected that accrual of 37 evaluable participants (6 for the lead-in, 6 who received M7824 as part of the initial investigation for PSA response and 25 homogeneously treated participants to evaluate PSA response) can be completed within 1 to 2 years. To allow for a small number of inevaluable participants, the accrual ceiling will be set at 40 participants.

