10.4 STATISTICAL ANALYSES

10.4.1 General approach

Following a safety determination in 6 participants meeting separate eligibility requirements, the PSA decline measured from the maximal value obtained while on study to the minimum value obtained while on study will be obtained for each patient, and will be considered a success if the maximal PSA decline is 30% or more. The fraction of evaluable participants who experience at least a 30% decline will be determined. Quantitative parameters will be tested for changes over time using paired tests.

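### The only comparison with untreated men uses a conservative Fisher test on the 30% PSA fraction and cannot register PSA slowing; use Boschloo's test and add a supporting log-PSA comparison

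*Combined protocol and SAP*

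**What the plan says.** Sections 10.2 and 10.4.3 propose about 36 men under surveillance on 16-C-0035 as an external control for a secondary evaluation. The general statement in 10.4.3 reads: "The changes in PSA on this trial during the initial 6 months can be compared to the changes in PSA during the initial 6 months". It refers to the 16-C-0035 surveillance arm and attaches no method. The only between-trial test named takes "The fractions of participants who experience a 30% PSA maximum change on the present study", together with the control fraction, and these "will be compared using a one-sided significance level Fisher's exact test".

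Section 10.4.3 gives no numerical level. Section 10.2 does: the planning calculation is made "with a 0.10 one-sided significance level". Its result is stated as "With 25 evaluable participants on this trial and 36 evaluable participants on the other trial, there would be 81% power"; the contrast assumed is 35% here against 10% among the controls.

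For this trial, section 10.4.1 defines success as a maximum-to-minimum fall: a man "will be considered a success if the maximal PSA decline is 30% or more". I read the between-trial fraction the same way, as a fall from a maximum to a later minimum.

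Change in PSA kinetics is a secondary objective (1.1.2, 10.1.2). Section 10.4.3 tests it with paired comparisons of each man's slopes after and before vaccine (two-tailed 0.05). No between-trial test of slope or log PSA is specified.

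**The concern.** Everything else in the efficacy analysis is single-arm or within-patient, apart from an informal contrast between treated men with and without M7824 (10.4.9). This comparison is therefore the only place where PSA on vaccine is set against PSA without treatment. Two features limit it.

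First, Fisher's test conditions on the total number of responders. In samples this small it leaves part of the nominal 0.10 unused.

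Second, a man whose PSA rises more slowly counts the same as a man whose PSA rises at its old rate. Section 1.2.3 cites an earlier Prostvac study in which median doubling time went from 5.3 to 7.7 months. An effect of that kind would leave the controlled comparison almost untouched. The paired slope tests could detect it, but without untreated men they cannot separate it from natural variation in PSA growth.

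**Working it through.** **Inputs.** From 10.2: n = 25 (this trial) and 36 (control), rates 35% and 10%, one-sided 0.10, Fisher's exact test, stated power 81%. From 1.2.3: doubling times 5.3 and 7.7 months. The documents give no SD or distribution for log PSA change, so anything that depends on one is an assumption.

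**1. The plan's own figure.** For each outcome (x of 25, y of 36), the Fisher p-value is the hypergeometric tail P(X ≥ x | total x + y). Power is the sum of Bin(x; 25, 0.35) × Bin(y; 36, 0.10) over outcomes with p ≤ 0.10.
- Power = 81.4%, which reproduces the stated 81%.

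**2. True size of Fisher's test.** The same sum with a common rate in both groups gives:
- 5.9% at 10%, 6.5% at 20% and 5.8% at 35%
- a maximum over all common rates of 6.6%, against the nominal 10%

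**3. Boschloo's test on the same counts.** It uses the Fisher p-value as the ordering statistic and takes the largest cutoff whose maximum size stays at or below 0.10.
- Critical Fisher p about 0.145; maximum size 9.9%
- Power at 35% v 10% = 83.6%, a gain of 83.6 − 81.4 = 2.2 points

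The gain is small because the two rejection regions coincide when five or fewer control men qualify. At a 10% rate, 36 × 0.10 = 3.6 are expected. The smallest outcome on which they differ is 8 of 25 v 6 of 36 (Fisher p = 0.138).

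**4. What the 30% cut misses.** Over 6 months at constant growth, PSA multiplies by 2^(6/DT).
- DT 5.3 months: 2^(6/5.3) = 2.19
- DT 7.7 months: 2^(6/7.7) = 1.72

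The ratio is 1.72/2.19 = 0.78. Neither man has a fall, so both score as non-responders apart from assay noise.

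**5. Power of a test on log PSA change, with assumed distributions.** Under a normal model with equal SDs, rates of 35% and 10% below the cut imply a shift of z(0.35) − z(0.10) = −0.385 + 1.282 = 0.896 SD. The standard error is √(1/25 + 1/36) = 0.260 SD, so power ≈ Φ(0.896/0.260 − 1.282) = 98%. Other models, each calibrated to 35% v 10%, with a one-sided 0.10 Welch test:

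| Model for log PSA change | Welch power |
|---|---|
| Equal-SD normal shift | 98% |
| Effect in 62.5% of men | 93% |
| Effect in 50% | 89% |
| Effect in 38.5% | 85% |
| Effect in 31.2% | 84% |
| Effect in 29.4% | 85% |
| Normal, treated SD 1.25 × control | 91% |
| Normal, treated SD 1.5 × control | 77% |
| Normal, treated SD 2 × control | 45% |

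**6. Exposure to imbalance.** Suppose there is no treatment effect, but mean doubling time is 10 months on this trial and 8 months on the control (assumed). The expected difference in 6-month log change is 6 × ln 2 × (1/8 − 1/10) = 0.104.
- SD 0.3: SE = 0.3 × 0.260 = 0.078; false rejection ≈ Φ(0.104/0.078 − 1.282) = 52%
- SD 0.6: SE = 0.156; false rejection ≈ Φ(0.104/0.156 − 1.282) = 27%

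Scoring the same net changes at the 30% cut and applying Fisher's test gives under 1% and 11%.

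**The case against.** The case for leaving the plan alone has real weight. The 30% fraction matches the primary endpoint, so the control arm supplies a background rate for it. The comparison is optional, secondary and non-randomised, with no decision attached. Kinetics are already analysed on a continuous scale within patients. The assumption-free gain from changing the test is 2.2 points. All of this stands and limits how much weight the point can carry.

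A reader might infer more from the findings than the documents support:

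- **That the stated power is wrong.** It is not; 81% reproduces.
- **That a log-PSA test would have 84-98% power with the same men.** That range holds only for equal-SD shifts or responder mixtures. Without an SD in the documents it is not a bound, and a treated spread of 1.5 times control or more brings power below Fisher's. The calculation also carries rates for a maximum-to-minimum fall over to a net change. A separate simulation of seven monthly values (assumed doubling times 5-15 months, log noise 0.138) kept the two variables distinct. With sustained falls in 30% of men, Welch on net change gave 81% against Fisher's 82%; with 45%, it gave 86% against 82%. When the fall had reversed by month 6, Welch gave about 10% and Fisher 82%.
- **That the fraction should be replaced as the main test.** Step 6 argues against this: mean log change responds directly to differences in baseline kinetics, while the 30% cut is much less sensitive to them.

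The objection leaves two gaps. Fisher's unused alpha can be partly recovered at no cost, and the paired slope tests have no untreated comparator. The open wording about comparing changes in PSA does not specify a continuous analysis; it leaves the method to be chosen later.

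**Conclusion.** The point holds in a limited form. The stated power is right, but Fisher's test runs at a true size of at most 6.6% where 10% was intended. Boschloo's test on the same counts raises power from 81.4% to 83.6% with size held at 9.9%. Those figures are exact and need only the plan's sample sizes, rates and level.

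The larger weakness is one of scope: the only controlled comparison cannot register slowing without a fall, although kinetics is a secondary objective. A supporting log-PSA analysis would fill that gap. Its power advantage cannot be promised, because it depends on a spread and shape that the documents do not give, and adjusting for pre-treatment kinetics reduces its exposure to imbalance without making the groups comparable in other respects. It belongs beside the responder fraction, not in its place. The primary single-arm analysis is unaffected.

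**What to change.** In section 10.4.3:

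1. Keep the 30% fraction as the tested quantity, state the one-sided 0.10 level there, and replace Fisher's exact test with Boschloo's.
2. Add a supporting between-trial comparison of log PSA change or slope, over the same defined window in both trials, adjusted for pre-treatment PSA doubling time or slope where available. Report it as a ratio of geometric means with its interval, next to the responder fractions. Define the window explicitly, because up to four monthly surveillance values may precede vaccine on this trial.

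In section 10.2, restate 81% as 84% for Boschloo's test. If a power figure is given for the log-PSA analysis, state its model and show the range: about 84-98% under equal-SD shift or responder-mixture models, about 77% at a treated SD of 1.5 times control and 45% at 2 times.

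The cost is revised wording and one further analysis. PSA values from both trials are needed anyway to compute the fractions; the adjustment also needs pre-treatment PSA from 16-C-0035, hence the qualifier. No patients or visits are added. The downside is that the log-PSA result is sensitive to baseline imbalance and can differ from the responder result, so the text should say beforehand that it is supportive.

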10.4.4 Safety Analyses

Safety of the combination regimen will be assessed by reporting the grade of adverse events noted in each participant, and reporting the fraction with grade 3 and grade 4 adverse events.

10.4.5 Baseline Descriptive Statistics

Demographic and clinical characteristics of all participants will be reported.

10.4.6 Planned interim analyses

None will be performed.

10.4.7 Subgroup analyses

None will be performed, except to consider exploratory evaluations based on the use of M7824

10.4.8 Tabulation of individual participant data

None will be provided.

10.4.9 Exploratory analyses

The study will aim to evaluate immune changes after treatment with 2 vaccines for 4 months.

Many immune parameters (See Section **5.1**) will be obtained at baseline and at several time points beginning at the time the two vaccines are first administered. The changes in the immune parameters after treatment with 2 vaccines for 4 months will be determined and tested for statistical significance using a two-tailed 0.05 significance level paired t-test or Wilcoxon signed rank test (if the paired differences are not normally distributed). Since there are potentially a moderately large number of these tests, they will be reported as being of secondary intent and presented without adjustment for multiple comparisons but in the context of the number of such tests performed.

Willing participants will continue to be followed after cycle 7 until progression or ADT is clinically indicated.

Patients in cohort 2 who received M7824 as part of their therapy will have their PSA response evaluated in a descriptive fashion, and may be compared informally to those from the remaining patients who do not receive M7824.

10.4.10

Halting Rules

If either of the below occurs, the Principal Investigator will halt accrual to the trial and will discuss with the NIH Intramural Institutional Review Board (IRB) whether any changes need to be made to the protocol.

- One occurrence of grade 5 toxicity by the NCI-CTCAE version 4.0 attributable to the treatment regimen.
- Two occurrences of grade 4 toxicity by the NCI-CTCAE version 4.0 attributable to the treatment regimen.
- More than two episodes of grade 3 colitis

This will apply to both cohorts—the phase I lead-in cohort and the main cohort of biochemical recurrence.

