Eligibility Criteria (for biochemical recurrence):

- Histologically confirmed adenocarcinoma of the prostate
- Participants with negative CT Scan and Tc-99m Bone Scan
- Participants with a PSA over 0.8 ng/ml for participants following radical prostatectomy or for participants following definitive radiation therapy: a rise in PSA of ≥ 2 ng/mL above the nadir
- Participants with a PSA doubling time of 5-15 months
- No history of active autoimmune disease or history of organ compromising autoimmune disease
- ECOG 0-1
- Safety lead-in cohort will evaluate 6 participants with castration resistant prostate cancer

Design:

- Three-arm, non-randomized study
- Accrual goal is a total of 37 evaluable participants (6 in an initial safety cohort, 6 participants who received M7824 as part of the initial investigation and 25 homogenously treated participants) to evaluate response
- Participants from an on-going study (NCT02649439) with nearly identical eligibility can serve as a contemporary control for secondary endpoints
- Following the safety lead-in, all participants will be enrolled and may undergo a surveillance period during which up to 4 consecutive monthly PSA values will be captured by the labs.
- After surveillance period, if applicable, participants will be treated with 2 vaccines concurrently, Prostvac and CV301, during months 1-4. For months 5-7, MSB0011359C [an anti-PD-L1 antibody (avelumab) with TGF β -Trap molecule] will be added to the regimen.
 - Effective with amendment v7/29/2021, MSB0011359C will no longer be given as part of the treatment combination for the Biochemical Recurrence cohort (Arms 2 and 3)
- Participants will be monitored for on-treatment and post-treatment PSA, immune and imaging responses.

SCHEMA

Prostvac: Q2 weeks for 1 month, then monthly for 6 additional months (7 months total)

CV301: Q2 weeks for 1 month, then monthly for 6 additional months (7 months total)

MSB0011359C: Given q 2 weeks for 3 months at phase II dose (flat dose of 1200 mg) starting after 4 months of vaccines. Effective with amendment v7/29/2021, MSB0011359C will no longer be given as part of the treatment combination for the Biochemical Recurrence cohort (Arms 2 and 3). This change is reflected in the new cohort 2 schema above.

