2.3.1 Treatment Assignment Procedures (for registration purposes only)

Cohorts

Number	Name	Description
1	Lead-In Cohort (closed December 2018)	Participants with advanced castration resistant prostate cancer (first six participants)
2	Biochemical Recurrence Cohort	Participants with biochemically recurrent prostate cancer

Arms

Number	Name	Description
1	Combination therapy (closed December 2018)	Prostvac + CV301 + MSB0011359C
2	Combination therapy + surveillance (closed)	Surveillance followed by Prostvac + CV301 then Prostvac + CV301 + MSB0011359C
3	Combination vaccine therapy +/- surveillance	Surveillance as needed followed by Prostvac + CV301

Arm Assignment

Participants in cohort 1 will be directly assigned to Arm 1 of the study. This cohort has been closed as of December 2018.

Participants in cohort 2 will be directly assigned to Arm 2, or Arm 3 of the study based upon time of enrollment. Participants enrolling after approval of amendment dated 7/29/2021 are assigned to Arm 3.

Please note: As of December 21, 2018, the 6 participants in the lead in cohort have completed the 6-week toxicity assessment period and no SAEs were seen. Per the protocol design participants will now be enrolled to the BCR cohort. The toxicity assessment of participants in the lead-in cohort is described in section [1.2.13](#).

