3 STUDY IMPLEMENTATION

3.1 STUDY DESIGN

This is a three-arm, open-label trial of combination immunotherapy in participants with biochemical recurrent prostate cancer. 37 evaluable participants will be enrolled (after the Safety Lead-In cohort with 6 participants (arm 1), 6 participants who received M7824 as part of the initial investigation for PSA response (arm 2), and 25 homogenously treated participants (arm 3) with an accrual ceiling of 40 participants.

A 6-participant phase I lead in cohort in advanced castration resistant prostate cancer participants will be conducted to determine safety. Dose levels for the lead in cohort are equivalent to the biochemical recurrence cohort. Participants will not have an observation period for the safety lead-in; dosing will begin after eligibility is confirmed (see Study Calendar in Section **18.2**).

Once all 6 participants have completed a 6-week toxicity assessment period the toxicity data will be shared with IRB before moving forward with the planned study in biochemical recurrence.

Participants may remain on treatment with vaccines in the lead in cohort as long as the participant is willing and their disease remains stable on follow-up imaging. As of December 21, 2018, the 6 participants in the lead in cohort have completed the 6-week toxicity assessment period and no SAEs were seen; therefore this cohort is closed.

Participants enrolled in Cohort 2 will undergo surveillance with four consecutive monthly PSA checks followed by Prostvac and CV301 during months 1-4 then Prostvac and CV301 during months 5-7.

- Existing participants with biochemical recurrent prostate cancer undergoing surveillance and PSA monitoring at the NIH may be enrolled at any point during the surveillance period provided the PSA monitoring is consistent with PSA monitoring in the Study Calendar (**APPENDIX C**) and the participant meets all other eligibility criteria. For example, if an eligible participant has 3 monthly PSA values, he may be enrolled onto the study, obtain one additional PSA value at a one month interval to complete the surveillance period, then

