¹⁵ For participants in the BCR cohort, two NaF PET Scans will be done when logistically feasible. These scans are for research purposes only. These scans will not be used to evaluate for clinical progression of disease.

¹⁶ Can be done any time prior to first treatment.

¹⁷ Surveys are optional at all time points and can be done as noted on study calendar, and every 3 months thereafter while participants are on-study. If surveys are not done, reason will be documented.

¹⁸ Participants will be asked to give stool samples during the surveillance period, after 3-4 months on treatment and after completion of 7 months of treatment (Section **5.2.3**). Note: These are optional.

¹⁹ When logistically feasible, PSMA PET scans should be done in the first two months during surveillance (or within 4 months of treatment initiation if surveillance period is shorter per Amendment v05/10/2023 and within 8 weeks after completing treatment. If PSMA PET is obtained within 8 weeks of starting surveillance, it will not need to be repeated during the surveillance period.

²⁰ With Amendment v05/10/2023, participants that have at least 3 PSA measurements in the surveillance period, with at least one of them sufficient to provide the doubling time from baseline, will not undergo any further PSA measurements in the surveillance period.

²¹ Participants starting treatment per Amendment v05/10/2023 with a surveillance period of 8 weeks or shorter do not need to repeat CT and Tc99 imaging on C1D1

Abbreviated Title: Combination Immunotherapy

Version Date: 05/10/2023

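### The halting rule stops accrual but not first doses, so a man already registered in the biochemical recurrence cohort can start treatment while the IRB reviews the trigger

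*Combined protocol and SAP*

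**What the plan says.** Section 10.4.10 (Halting Rules) lists three triggers: one grade 5 toxicity attributable to treatment, two attributable grade 4 toxicities, or more than two episodes of grade 3 colitis. If one occurs, "the Principal Investigator will halt accrual to the trial and will discuss with the NIH Intramural Institutional Review Board (IRB" whether the protocol needs changing. The same wording governs "the phase I lead-in cohort and the main cohort of biochemical recurrence".

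The two cohorts reach their first dose differently.

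- **Lead-in (Section 3.1):** "Participants will not have an observation period for the safety lead-in; dosing will begin after eligibility is confirmed".
- **Biochemical recurrence (Précis, Design):** "all participants will be enrolled and may undergo a surveillance period during which up to 4 consecutive monthly PSA values" are collected, and treatment comes afterwards. The calendar in Section 18.1 places consent and registration in the screening column, ahead of four surveillance columns and C1D1.
- **Worked example (Section 3.1):** a man already followed at NIH enrols with three PSA values, must "obtain one additional PSA value at a one month interval to complete the surveillance period", and only then starts C1D1.

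The interval is not always long. Section 2.3.1 describes Arm 3 as "Surveillance as needed followed by Prostvac + CV301". Under footnote 20 of Section 18.1, men with at least three suitable PSA values "will not undergo any further PSA measurements in the surveillance period". On pace, Section 10.2 states: "It is anticipated that 1-2 participants per month can be enrolled onto this trial".

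**The concern.** A halting rule of this kind is meant to prevent new exposure while a serious signal is assessed. Stopping enrolment achieves that only where enrolment and first dose nearly coincide, as they did in the lead-in. The same sentence was carried over to a cohort in which they can be up to four months apart. There it does not reach men who are registered and waiting.

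C1D1 includes Prostvac-V, a single priming dose that cannot be withdrawn once given. Section 14.2.1 notes that its vaccinia vector can replicate in mammalian cells and that systemic infection is possible. At stake is an avoidable first exposure in an asymptomatic man, after an event as serious as a treatment-related death and before the IRB has decided whether the protocol should change.

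**Working it through.** The point turns on wording and rests on no figure in the plan. There are two checks: whether other text closes the gap, and how many men could fall into it.

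**Other text that might hold C1D1**

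| Section | What it provides | Holds another man's C1D1? |
|---|---|---|
| 3.1.1 | 6 weeks between C1D1 of the third and fourth participants | Once only; not triggered by toxicity |
| 3.3.2, 3.6.1, 4.2.4 | Delay, removal or holding of agents for toxicity | Read naturally, only the man with the event |
| 7.5.1 | Weekly adverse event review; accrual interrupted or documents changed | No |
| 12.4.5 | Significant new findings explained to participants | No |
| 13.1 | Study may be suspended | Possible, but discretionary and not linked to these triggers |

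Section 3.1.1 shows that the protocol can restrict C1D1 separately from enrolment when that is intended.

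**Men affected, given a trigger**

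Inputs:
- Planned enrolment rate: 1 to 2 per month (Section 10.2).
- Gap from registration to C1D1: 0 to 112 days (four 28-day months, Section 18.1).
- IRB review length: not in the documents; 14 to 28 days assumed, with 56 days as a stress case.
- Month: 30.44 days.
- Slow rate: six men received M7824 between 21 December 2018, when the recurrence cohort could open, and the amendment of 29 July 2021. That is 951 days, and 951/30.44 = 31.24 months, so 6/31.24 = 0.192 per month. A man enrolled in the last 224 days (112 of surveillance plus 112 of vaccines) would not yet have reached M7824. Excluding those days gives 727/30.44 = 23.88 months and 6/23.88 = 0.251 per month. Both figures assume that these six men approximate enrolment.

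Expected men reaching C1D1 during the review = rate × min(review, gap)/30.44.

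Example: 1 × 14/30.44 = 0.46; 2 × 28/30.44 = 1.84.

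| Rate per month | 14-day review, gap ≥ 28 d | 28-day review, gap ≥ 28 d | 56-day review, gap ≥ 56 d |
|---|---|---|---|
| 1 | 0.46 | 0.92 | 1.84 |
| 2 | 0.92 | 1.84 | 3.68 |
| 0.192 | 0.09 | 0.18 | 0.35 |
| 0.251 | 0.12 | 0.23 | 0.46 |

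With a gap of 0 days the result is 0 at any rate. A check at the planned rates, with evenly spaced registrations and a random trigger time, gave the same means to within 0.01 for 14- and 28-day reviews and gaps of 28, 56 and 112 days.

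**Chance that at least one man is affected, given a trigger**

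With Poisson registration this is 1 − exp(−expected men).

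- Planned pace, 14 to 28 day review: 1 − exp(−0.46) = 37% to 1 − exp(−1.84) = 84%.
- Slow pace, same review: 1 − exp(−0.09) = 8% to 1 − exp(−0.23) = 21%.

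**The case against.** The strongest reply is that a first dose during the review would require the investigator, the sponsor and the IRB all to decline to act. Section 13.1 lists unexpected, significant or unacceptable risk among the grounds for suspension. Once suspended, the study resumes only when the sponsor, the IRB and, where applicable, FDA are satisfied. Serious events reach the sponsor's safety office within 24 hours (8.3). Deaths within 30 days of a research intervention and not due to progression reach the Clinical Director within one business day (7.3). Unexpected fatal or life-threatening Prostvac events reach the biosafety committee within 7 days (7.4.1). IRB handling also follows policies cited in Section 7.2 that are not reproduced here. All of this makes a hold likely in practice, but nothing in the visible text makes it automatic.

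A second objection is that the planned-pace figures lean high. That stands. Section 10.2 expected accrual to finish in 1 to 2 years, yet the lead-in assessment was complete by December 2018 and surveillance was still being amended in May 2023. The slow-pace figures may be nearer the truth, and shortened surveillance can bring the gap close to zero. A trigger is also less likely without M7824, and Section 1.2.4 reports no grade 3 or higher toxicity among 12 patients in the CV301 phase I study.

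A third is that holding only C1D1 leaves men already on treatment unaddressed. That is also true: 10.4.10 is silent on them. Continuing an established course calls for individual clinical judgment, whereas deferring a first dose is simple.

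**Conclusion.** The concern holds. As written, 10.4.10 permits a registered, undosed man in the biochemical recurrence cohort to receive C1D1 after a trigger and before the IRB review ends, and no other visible section requires a hold. Confidence in that reading is high. How often it would matter in practice is less certain, because the IRB policies cannot be seen and the documents do not allow the probability of a trigger to be estimated.

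Given a trigger, a 14 to 28 day review and a gap of at least 28 days, the expected number is roughly 0.5 to 1.8 men at the planned pace and 0.1 to 0.2 at the slow pace. It is near zero where surveillance was completed before registration. This is a cheap improvement to participant safety. It is not a flaw in the design, the primary endpoint or the power.

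**What to change.** Replace the lead sentence of 10.4.10 with wording to this effect:

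> If any of the events below occurs, the Principal Investigator will halt new registrations, will not give C1D1 to any registered participant who has not yet been dosed, and will discuss with the IRB whether the protocol needs to change. Both holds remain until the IRB review is complete.

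This keeps the existing duty to consult the IRB. It also replaces the present wording for two alternatives, since three triggers are listed. A further sentence stating who decides on continued dosing for men already on treatment would be useful but is not essential.

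The cost is one sentence, with practical effects only after a trigger:

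- Some C1D1 visits are delayed. Section 18.1 already lets surveillance visits slip by up to 2 weeks for logistical reasons.
- Baseline tests have a 16-day window before treatment and may need repeating.
- Footnote 21 of Section 18.1 waives repeat CT and bone scans at C1D1 only when surveillance is 8 weeks or shorter, so a hold running past that could require new scans.
- Any PSA values taken during the hold could enter the apex in Section 6.3.2, the maximum used in Section 10.4.2, and the pre-treatment slope. Hold dates should therefore be recorded and reported for the men concerned.

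Sample size, alpha and power do not change.
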